Study title: Sleep quality in COPD patients. A clinical and polysomnographic study.

Project number: PR(AG) 365/2015

Date of the document: June/10/2016

Hypothesis

The CASIS questionnaire is an appropriate tool to measure the sleep quality abnormalities to be detected by polysomnography

Objetives

1. To know the validity of the CASIS questionnaire as a predictor of objective sleep alterations measured by polysomnography in patients with COPD.
2. To know the relationship between the evaluation of nocturnal symptoms by the CASIS and the Pittsburgh questionnaires in patients with COPD.
3. To know the relationship existing between the CASIS punctuation and several variables of COPD patients (phenotype, physical activity, lung function and exacerbations).

A.) Subjects

The study will be carried out in the Respiratory Service of the Vall d'Hebron University Hospital in Barcelona. Consecutive patients aged 40-80 years, smokers or exsmokers of at least 10 pack-years, diagnosed with moderate-to-severe COPD (post bronchodilator FEV1% < 70% and FEV1 ≥ 30 but < 80% of predicted in a spirometry performed within 6 months prior to inclusion into the study). The study protocol will be approved by the institutional review board and informed written consent will be obtained from all participants.

Exclusion criteria:

- a.) Non-stable COPD. Stability is defined as being exacerbation free and without treatment changes for at least 4 weeks prior to baseline evaluation. The presence of a COPD exacerbation previous to the sleep studies (polysomnography, actigraphy, OSLER test) will lead to an early discontinuation of the patient's participation in the study.
- b.) Heart failure, asthma, cancer or other major medical illness with known effects on sleep quality.
- c.) Unable to understanding the questionnaires administered in the study.
- d.) Known Obstructive Sleep Apnea, other sleep disorder (narcolepsy, periodic limb movements) or shift work.
- e.) Chronic respiratory failure (PaO2 <60 mmHg).
- f.) Treatment with sedatives or antidepressants.

B.) Measures

Patient's characteristics and physical examination at baseline: it will include documentation related to age, sex, height, weight, alcohol consumption, tobacco use, current medications,

date of the last COPD exacerbation and forced spirometry. No interference with current medications and patient's usual medical care will be undertaken during the study.

Symptoms and neurobehavioural examinations:

- Epworth sleepiness scale
- Sleep habits. Daily Sleep diary
- Pittsburgh Sleep Quality Index
- COPD and Asthma Sleep Impact Scale (CASIS)
- Night and early morning COPD symptoms scale (NiSCI, EMSCI)
- COPD Assessment Test (CAT)
- Hospital Anxiety and Depression Scale (HAD)
- mMRC dyspnea scale
- Charlson's comorbidity index
- Specific evaluation of comorbidities that can influence sleep quality: prostatism, pain, etc.

C.) Polysomnography

[figure not shown]
Overnight sleep study will be conducted at the Multidisciplinary Sleep Unit using a computerized polysomnography device (Compumedics E Series, Australia). Polysomnography will include recordings of six electroencephalographic channels, bilateral electro-oculograms, chin and tibial electromyogram, electrocardiogram, airflow by nasal pressure transducer and oronasal thermocouples, as well as oxygen saturation by finger pulse oximeter. An expert scorer blinded to the study will review all sleep studies manually. According to standard definitions (American Sleep Disorders Association criteria) the following variables will be obtained:

- 1.) Total sleep time
- 2.) Sleep efficiency
- 3.) Sleep architecture
- 4.) Arousal Index
- 5.) Respiratory variables. Apnoea-hypopnoea index. Four oxygen saturation measures will be assessed: the cumulative percentage of time spent with oxygen saturations below 90% (CT90), and the basal, lowest and mean nocturnal SaO₂. In addition, the oxygen desaturation index (ODI) per hour will be calculated by dividing the total number of oxygen desaturation events by the total hours of sleep. Four different oxygen desaturation thresholds (reductions in SaO₂ equal or greater than 2%, 3%, 4%, and 5%) as indicators of hypoxemia severity (ODI-2%, ODI-3%, ODI-4%, and ODI-5%) will be determined.

D.) Study design

1. This will be an observational study with the objective of knowing the validity of the CASIS questionnaire as a predictor of objective sleep alterations measured by polysomnography in patients with COPD.

Flow chart of study assessments:

* Good and bad sleepers will be defined according to CASIS scores according to previous data in our population

**Plus actigraphy the week before and the Oxford sleep resistance test (OSLER) the morning after the sleep study.

Confidentiality: Confidentiality will be of the utmost importance throughout the study. Computerized files will have a numerical code for each patient. Only the study investigators will have access to this information by using a password. Eventually and without any violation of confidentiality, the Vall d'Hebron Hospital Ethics Committee of Clinical Investigation and Regulatory Authorities could have access to patient's data in order to supervise the study procedures

Visits: 1- Recruitment and spirometry (1 week before polysomnography)

2- Actigraphy

3- Polysomnography and OSLER test

Number of patients needed

The main variable of the study is sleep efficiency. We consider a 15% difference between good and bad sleepers as clinically relevant. According to previous published data on sleep efficiency in COPD patients, a sample size of 29 patients in each group (total 58 patients) is estimated to provide at least 90% power to detect the chosen difference.

Based on this sample size calculation, the following procedures will be performed:

- 1- Polysomnography: 58
- 2- Actigraphy: 58
- 3- Osler's test: 58
- 4- Spirometry: 200 (estimated) (to evaluate potential study candidates in the first visit)

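### Does the undefined FEV1% in the COPD entry criterion leave it unclear who can be enrolled?

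*Protocol*

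**What the plan says.** Section A.) Subjects recruits consecutive patients "diagnosed with moderate-to-severe COPD" and adds the spirometric limits in brackets: "post bronchodilator FEV1% < 70% and FEV1 ≥ 30 but < 80% of predicted". The first limit is written on FEV1%, with no statement of what it is a percentage of. The second is written on FEV1 and is expressly relative to the predicted value.

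Spirometry is mentioned elsewhere without a variable or threshold. Section B.) Measures lists "date of the last COPD exacerbation and forced spirometry" among the baseline items. The visit list opens with "Recruitment and spirometry (1 week before polysomnography". The procedure counts under Number of patients needed include "Spirometry: 200 (estimated) (to evaluate potential study candidates in the first visit". Lung function returns once more as an analysis variable: the third objective relates the CASIS score to "phenotype, physical activity, lung function and exacerbations".

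**The concern.** Both limits appear to be set on FEV1. If the words about the predicted value are taken to govern both halves, the first limit is a second and stricter ceiling on the same quantity. Patients at 70 to below 80% of predicted would then be refused by one half of the sentence and admitted by the other, and no spirometric condition would establish airflow obstruction. The intended term could be a ratio of FEV1 to FVC, but the document never names one.

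Entry criteria belong in the protocol, so this cannot be left to an analysis plan. If the narrower reading were applied at the first visit, the mildest part of the intended population would be lost. The validation of CASIS would then apply to a different group, and the lung-function analysis in the third objective would lose the upper end of its range.

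**Working it through.** No sample-size, power or significance figure rests on this wording, so there is no figure of the plan's own to reproduce. The check compares the two readings as sets and then asks which one the sentence supports.

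**Inputs** (Protocol, A.) Subjects): first limit "post bronchodilator FEV1% < 70" per cent; second limit "FEV1 ≥ 30 but < 80% of predicted". Let F be FEV1 as a percentage of predicted, and R an FEV1 ratio expressed as a percentage.

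**Reading 1, both limits on F.** F < 70 and 30 ≤ F < 80 gives 30 ≤ F < 70. The 80% limit never binds. The stated range of 80 − 30 = 50 points becomes 70 − 30 = 40 points, a loss of 10 of 50.

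**Reading 2, first limit on R.** R < 70 and 30 ≤ F < 80. Both limits bind, and the full 50 points remain.

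**Where they differ** (illustrative values, assumed):

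| Patient | Reading 1 | Reading 2 |
|---|---|---|
| F = 75, R = 65 | out (75 ≥ 70) | in (65 < 70; 30 ≤ 75 < 80) |
| F = 65, R = 75 | in (65 < 70; 30 ≤ 65 < 80) | out (75 ≥ 70) |

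The disagreement is therefore confined to F from 70 to below 80 with R below 70, and F from 30 to below 70 with R of 70 or more.

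**Which reading the text supports.**

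1. The sentence uses two labels, FEV1% and FEV1. Had one quantity been meant, a single label and a single range would have sufficed.
2. The reference to predicted values follows the second limit. Reading 1 has to carry it back across the conjunction to the first.
3. Reading 1 leaves the 80% limit without effect. Reading 2 gives each half a task: obstruction first, then severity.
4. The bracket qualifies a diagnosis of COPD. An obstruction test belongs there, and only Reading 2 supplies one.

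**Can the number of affected patients be found?** No. The protocol estimates 200 spirometries and plans 58 polysomnographies, but candidates may also fail on age, smoking history or any of the six exclusion criteria. The gap between those counts says nothing about this wording.

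**Does the main comparison depend on it?** No. The sample size is built on a 15% difference in sleep efficiency between good and bad sleepers, with 29 per group (2 × 29 = 58) and at least 90% power. No spirometric quantity enters.

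**The case for a change.** The strongest opposing argument is that an eligibility rule should be reproducible from the page by a screener, an ethics committee or a later reader, and this one is not: its first term is undefined and no other section supplies the definition. Leaning on the COPD diagnosis is close to circular, because the bracket is what the protocol offers to define that diagnosis. The diagnosis reduces the risk of enrolling patients without obstruction, but it does nothing for patients at 70 to below 80% of predicted who would be wrongly refused. The correction would be one line.

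Much of this stands as a matter of drafting. The denominator is missing, and nothing at that point suggests a redaction or a fault in the text. It is also true that the diagnosis protects against only one of the two kinds of misclassification. What does not stand is the step from an undefined label to a realistic risk of wrong enrolment. That step requires the staff of a single respiratory service to adopt the reading that cancels their own upper limit, and nothing in the document suggests that they would. The loss of the upper FEV1 range from the third objective depends wholly on the same step, and lung function is one of four variables named there.

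**Conclusion.** The observation is accurate, but no change to the plan follows. FEV1% is an undefined abbreviation, most plausibly shorthand or a slip for an FEV1 ratio, and only that reading leaves every part of the criterion with a function. Those who apply it would fill the gap sensibly.

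The most that could be at stake is 10 of the 50 points of the FEV1 range, plus patients with a ratio of 70% or more whom the required diagnosis already makes unlikely. The number of patients cannot be derived. The sample size of 58, the power and the analysis of sleep efficiency are the same under either reading.

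This conclusion assumes that screening is done by respiratory clinicians at the one named hospital, as section A.) Subjects states, and that they apply the coherent reading. Evidence that candidates at 70 to below 80% of predicted were being refused on the first limit would reopen the point.

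### Does excluding only known sleep apnoea leave the comparison of sleep efficiency distorted by cases first found on the study polysomnogram?

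*Protocol*

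**What the plan says.** Criterion d in section A.) Subjects excludes "Known Obstructive Sleep Apnea, other sleep disorder (narcolepsy, periodic limb movements) or shift work". The word for a prior diagnosis stands directly before sleep apnoea. Whether it also governs the limb-movement item is a matter of reading.

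The visit list puts "Recruitment and spirometry (1 week before polysomnography", and no sleep test is described before enrolment. The only event that the text names as ending participation is an exacerbation before the sleep studies, which "will lead to an early discontinuation of the patient's participation in the study".

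Section C.) Polysomnography lists, as item 5, "Respiratory variables. Apnoea-hypopnoea index", together with the saturation measures and four desaturation indices. The montage includes "chin and tibial electromyogram", but no limb-movement index appears among the listed variables.

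On the comparison itself, the sample-size section says "The main variable of the study is sleep efficiency", and a note to the flow chart says "Good and bad sleepers will be defined according to CASIS scores according to previous data in our population". The sample size is 29 per group, 58 in total, for a 15% difference with at least 90% power, and 58 polysomnograms are planned. The protocol names no test, model, covariate or analysis set. The flow chart itself is not reproduced in the text at hand.

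**The concern.** The exclusion appears meant to keep other causes of poor sleep out of the sample, yet for apnoea it reaches only patients who already carry the diagnosis. One week after recruitment the study measures AHI in everyone, so it will probably find some of the condition it tried to exclude. The text gives no instruction for that case. Because the planned number of polysomnograms equals the number needed, it is natural to assume that everyone stays in.

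If unrecognised apnoea or limb-movement disorder lowers sleep efficiency and is more frequent in one CASIS group, it would widen or narrow the difference between the groups. A reader might then credit the questionnaire with detecting COPD-related sleep disturbance when part of the contrast came from another disorder. The missing limb-movement index adds to the impression, since that exclusion cannot be checked from the listed outputs.

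**Working it through.** **1. What the text supports.**

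| Element of the concern | What the protocol contains |
|---|---|
| Only diagnosed apnoea is excluded | Yes, criterion d |
| Only diagnosed limb-movement disorder is excluded | One reading; that item has no qualifier of its own |
| AHI available for every patient | Yes, section C.), item 5 |
| Limb-movement data available | Raw tibial signal only; no index listed |
| Cases stay in the comparison unadjusted | Not stated; no model, covariates or analysis set are given |

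The last row carries the concern, and it is an inference from silence.

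**2. The question being asked.** Objective 1, repeated under D.) Study design, concerns CASIS as a predictor of objective alterations on polysomnography among COPD patients. It does not restrict the cause of those alterations. AHI, the arousal index and the desaturation indices are themselves listed polysomnographic results. A patient with unrecognised apnoea who scores badly on CASIS and sleeps inefficiently is a correct prediction under this objective. The contrast would count as biased only if the target were alterations attributable to COPD alone.

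**3. The plan's own figure.** SD and alpha are not stated, so 29 per group can only be solved backwards. I read 15% as 15 percentage points and assume a two-sided alpha of 0.05.

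- Normal approximation: SD = 15 / [√(2/29) × (1.960 + 1.282)] = 17.6.
- Two-sample t-test (noncentral t): SD = 17.3, with power of 90.1% at 29 per group.

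This agrees with the stated sample size by construction and does not confirm it independently.

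**4. Size under assumptions.** Neither prevalence nor effect is in the documents. Let the disorder lower sleep efficiency by e points.

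- Shift in the group difference = e × (prevalence in bad sleepers − prevalence in good sleepers).
- Inflated SD = √[17.3² + mean of p(1 − p) × e²]. For 30% and 10%, the mean of p(1 − p) is (0.21 + 0.09)/2 = 0.15. For 20% in both groups it is 0.16.

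| e (points) | 30% bad, 10% good: shift | As share of 15 | 10% bad, 30% good: power for a true 15 | 20% in both: power |
|---|---|---|---|---|
| 5 | +1 | 7% | 85% | 89.7% |
| 10 | +2 | 13% | 78% | 88.5% |
| 15 | +3 | 20% | 69% | 86.6% |

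The third pattern, with no difference in prevalence, gives no shift at all. The marked losses of power require three times as many disordered sleepers among the good sleepers as among the bad, and nothing in the protocol suggests that. The calculation also adds the disorder's variance to 17.3. If the published COPD data behind the sample size already included undiagnosed cases, that variance is counted twice.

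**5. Cost of removing such patients.** With SD 17.3 and 15 points, removing 10%, 20% or 30% of the 58 leaves 26.1, 23.2 or 20.3 per group on average, and power of about 87%, 82% or 77%. Exclusion on AHI therefore has its own price in a study with 58 planned recordings.

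**The case for a change.** The best case for the concern is that this is a matter of eligibility and measurement, which a protocol fixes, and not only of analysis. The study's own recording can show that an enrolled patient has the excluded disorder, and the text is silent on what follows. Scoring is manual, so an index left off the list may mean reading the recordings again. An AHI cut-off chosen after sleep efficiency has been seen would be open to selection. A sensitivity analysis beside the all-patient result would cost little and would leave the main comparison untouched.

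The factual parts stand: no rule is written for disorders found on the polysomnogram, and no limb-movement index is listed. They do not amount to an error. Excluding patients with a prior diagnosis while recording AHI in everyone is a coherent way to study COPD patients not known to have apnoea, and criterion d is not contradicted when the recording finds more. A limb-movement index can still be scored from the tibial signal. Cut-offs and sensitivity analyses are commonly set in the SAP, and the SAP is not shown. Whether to adjust for AHI at all is a choice on which statisticians would differ, because AHI is one of the outcomes the questionnaire might reflect.

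**Conclusion.** The concern does not hold. The protocol does not say that patients with newly found apnoea or limb-movement disorder are compared without adjustment; it describes no analysis model. Keeping them fits the stated objective, and adjusting for or excluding on AHI could remove signal that the study sets out to validate. What remains is absent detail of a kind commonly left to the SAP, together with a preference for one more scored index.

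No size can be derived from the documents. The illustrative shift of 1 to 3 points, and the power range of 69% to 85% in the reverse pattern, rest on assumed prevalences, an assumed effect of 5 to 15 points, an assumed two-sided alpha of 0.05 and an SD of 17.3 solved backwards from 29 per group. With equal prevalence there is no shift, and power stays between 86.6% and 89.7%. This judgement would change if the stated aim were confined to sleep alterations attributable to COPD alone.

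### Objective 1 asks how well CASIS predicts polysomnographic sleep alterations, but the one comparison fixed and sized is a two-group contrast that discards information in the score and does not measure prediction

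*Protocol*

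**What the plan says.** Objectives, item 1, of the Protocol sets the aim: "To know the validity of the CASIS questionnaire as a predictor of objective sleep alterations measured by polysomnography in patients with COPD". Section D (Study design), item 1, repeats it: "This will be an observational study with the objective of knowing the validity of the CASIS questionnaire as a predictor of objective sleep alterations".

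The section on the number of patients needed names one main variable and one benchmark: "The main variable of the study is sleep efficiency. We consider a 15% difference between good and bad sleepers as clinically relevant". It sizes the study on that contrast: "a sample size of 29 patients in each group (total 58 patients) is estimated to provide at least 90% power".

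The flow-chart footnote in section D shows how the two groups arise: "Good and bad sleepers will be defined according to CASIS scores according to previous data in our population". The grouping variable is therefore the predictor under study, reduced to two levels.

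Objectives, item 3, works with the score itself: "To know the relationship existing between the CASIS punctuation and several variables of COPD patients". So the full CASIS score is collected and available for every patient.

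**The concern.** The stated question and the sized comparison are not the same. Objective 1 asks how well a questionnaire score predicts a polysomnographic result. The sized comparison asks whether two CASIS groups differ in sleep efficiency. A yes to the second question supports validity, but it leaves the strength of prediction unmeasured.

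Two things are at stake. First, if objective 1 were concluded from the group contrast, a significant difference could be reported as predictive validity without any estimate of how strong the prediction is. Second, cutting a continuous predictor in two treats everyone on the same side of the cut alike, which costs power when the relation is roughly linear. The continuous score avoids both problems at no extra measurement cost.

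**Working it through.** **Inputs from the Protocol.** Difference 15%; 29 per group, 58 in total; power at least 90%. The SD, the significance level, the sidedness and whether 15% is absolute or relative are not given. I assume a two-sided 5% test and 15 absolute points. That the contrast is one of means is also inferred.

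**1. The plan's own figure.** Without an SD, 29 per group can only be solved backwards.
- Normal approximation: SD = 15 × √(29/2) / (1.960 + 1.282) = 57.12 / 3.242 = 17.6.
- With the t-test the limit is SD 17.3, a standardised difference d = 15/17.3 = 0.866.
- With 29 per group, t-test power is about 98.0% at SD 14, 99.7% at SD 12 and 99.99% at SD 10. At SD 20 it falls to about 80%.

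So 29 per group fits the claim of at least 90% power for any SD up to about 17.3, and nothing shows the number to be wrong.

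**2. What the planned contrast says about prediction.** Take d = 0.866, where power is exactly 90%. The correlation of two-level group membership with sleep efficiency is d/√(d² + 4) = 0.866/√4.750 = 0.397. Group membership then explains 0.397² = 0.158, about 16% of the variance. A difference of the size the protocol calls relevant can thus go with quite modest prediction.

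**3. Gain from the continuous score: unselected patients, median split.** Assume a linear bivariate normal relation. Splitting at the median multiplies the correlation by √(2/π) = 0.798, so the underlying correlation is 0.397/0.798 = 0.498.
- Fisher z: artanh(0.498) = 0.547; 0.547 × √(58 − 3) = 4.05; 4.05 − 1.96 = 2.09; power about 98%.
- Simulation with 20,000 data sets: 89% for the split t-test, 98% for the continuous test.

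**4. Gain if the groups come from the CASIS extremes.** With 29 patients from each extreme tertile, two-group power near 90% corresponds to a correlation of about 0.38, not 0.50. Simulated power is about 91% for the two-group test and 96% for the continuous test.

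**5. Gain if the SD is smaller.** At SD 14 or below, step 1 already gives the two-group test 98% or more, so almost nothing is left to gain in power.

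**6. Why the slope should lead.** Under extreme-tertile sampling a true correlation of 0.498 averages about 0.57 in the sample, because selection on CASIS widens its spread. If the relation is linear, the slope of sleep efficiency on CASIS is not biased by selection on CASIS.

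**7. Precision of an AUC.** The Hanley–McNeil 95% half-width with 58 patients, for an AUC between 0.65 and 0.75, is 0.142 to 0.126 with a 29/29 division by the sleep-efficiency threshold and 0.154 to 0.140 with 20/38. That is roughly ±0.13 to 0.15, too wide to carry the main claim.

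**The case against.** The strongest reply is that nothing here is stated wrongly. The section on patient numbers sizes the study; it does not say that objective 1 will be judged by that test alone. A statistical analysis plan may specify regression, correlation or ROC analysis, and item 3 of the objectives shows that the score will be used. This stands in part: the point is not that other analyses are absent. It is that the main comparison, the relevance benchmark and the justification of 58 are all tied to a contrast that does not answer objective 1.

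The size of the gain is also open to challenge. The cut-off comes from earlier data, not the sample median, and exactly 29 per group suggests quotas, although consecutive recruitment points the other way. The flow chart that might settle this is not readable. This stands in full, so the gain is given for more than one sampling scheme.

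A reader might infer three stronger things that the documents do not support:
- That about 38 patients would have sufficed. This holds only for an unselected median split with two-group power at exactly 90%.
- That the raw correlation can be read directly as strength of prediction. It is inflated if patients are selected on CASIS.
- That a just-significant result, equivalent to an AUC of about 0.65, exposes a flaw particular to this protocol. Any design sized for 90% power has a significance boundary below its planned effect.

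**Conclusion.** The point holds as a mismatch between objective and main comparison, with a better method available from data already planned. It is not an arithmetic error, and it would be wrong to conclude that 58 is too few or too many: the number fits its stated power for any SD up to about 17.3 points.

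The power gain from the continuous score is about 90% to 98% (median split, correlation near 0.50), about 91% to 96% (extreme tertiles, correlation near 0.38), and near nil if the unstated SD is clearly smaller. These figures rest on a two-sided 5% test, 15 absolute points and a linear bivariate normal relation. The other gain does not depend on the SD: the main result becomes an estimate of how sleep efficiency changes with CASIS, which is closer to what objective 1 asks. The change is worth making, with medium confidence because the sampling scheme and the SD are not stated.

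**What to change.** In the Protocol, state that objective 1 is judged mainly by the regression of polysomnographic sleep efficiency on the continuous CASIS score, reported as a slope with 95% confidence interval. Then:

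- Report the correlation with 95% confidence interval only if patients are not selected on CASIS, or after correction for that selection.
- Keep the difference between good and bad sleepers as supportive known-groups evidence, together with the existing sample-size argument.
- If wanted, report as descriptive the AUC of CASIS for a sleep-efficiency threshold fixed in advance, and state its wide interval (about ±0.13 to 0.15).

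The cost is wording only: no added patients, visits or measurements. The downsides are that the analysis assumes a roughly linear relation, which should be checked, and that the validity claim becomes more modest. An AUC would also require a threshold to be chosen and justified beforehand.

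### Do the counts of exactly 58 for each sleep test need an allowance for loss or a stated replacement rule?

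*Protocol*

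**What the plan says.** Under Number of patients needed: "The main variable of the study is sleep efficiency". The target difference follows: "We consider a 15% difference between good and bad sleepers as clinically relevant". The number is attributed to earlier literature ("According to previous published data on sleep efficiency in COPD patients") and given as "a sample size of 29 patients in each group (total 58 patients) is estimated to provide at least 90% power". The SD and the significance level are not stated.

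The list of procedures is then derived from that number: 58 polysomnographies, "Actigraphy: 58" and 58 OSLER tests. The one larger entry is "Spirometry: 200 (estimated) (to evaluate potential study candidates in the first visit").

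Two other places bear on loss after inclusion:

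- Exclusion criterion a.): "The presence of a COPD exacerbation previous to the sleep studies (polysomnography, actigraphy, OSLER test) will lead to an early discontinuation" of participation. The same criterion requires at least 4 weeks of stability before the baseline evaluation.
- The flow chart footnote in D.) Study design: "Plus actigraphy the week before and the Oxford sleep resistance test (OSLER) the morning after the sleep study". The visit list agrees, with recruitment and spirometry 1 week before polysomnography, then actigraphy, then polysomnography and OSLER in one visit.

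A second footnote says that good and bad sleepers are defined by CASIS score, using earlier data from the same population. The flow chart itself was not readable in the text available here.

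**The concern.** The protocol foresees that some included patients will stop before polysomnography, yet its test counts leave no room for this. A patient who has an exacerbation between actigraphy and polysomnography uses an actigraphy and gives no value for sleep efficiency. Read literally, equal counts of 58 fit only if nobody is lost between the two tests and no recording is unusable.

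The groups also form from CASIS scores in consecutive patients, not by allocation, so 29 and 29 does not arise by itself. The readable text does not say how each group is filled or whether a lost patient is replaced. If 58 meant patients started, fewer than 29 per group could be analysed, and power for the main comparison could fall below the stated 90%.

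**Working it through.** **1. Counts.** 2 × 29 = 58, the figure given for each of the three sleep tests. The built-in allowance is 58 − 58 = 0.

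**2. The plan's own figure.** Inputs from the protocol: difference 15%, 29 per group, power at least 90%. Assumptions: 15% means 15 percentage points, and the test is two-sided at 5%. The SD is missing, so 29 cannot be reproduced independently. It can only be solved backwards.

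- Normal approximation: SD = 15 / [(1.96 + 1.2816) × √(2/29)] ≈ 17.6 points. In the other direction, SD 17.5 gives n = 2 × (17.5 × 3.2416 / 15)² = 28.6, which rounds up to 29.
- Noncentral t with 56 degrees of freedom: 90% at 29 per group needs d = 0.866, so SD = 15 / 0.866 ≈ 17.3 points.
- If 28 per group already gave 90%, d would be 0.882 and SD = 15 / 0.882 ≈ 17.0 points.

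So if 29 is the smallest group size that reaches 90% by the t-test, the planning SD lay between about 17.0 and 17.3 points. The figure of 29 is attainable and is not shown to be wrong.

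**3. Loss without replacement.** The protocol gives no loss rate; 10% is an assumption for illustration. 29 × 0.9 = 26.1, so take 26 per group. Power comes from the noncentral t with noncentrality 15 / (SD × √(2/n)).

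| Planning SD (points) | 29 per group | 28 per group | 26 per group |
|---|---|---|---|
| 17.3 (d = 0.866) | 90.0% | 88.9% | 86.5% |
| 17.0 (d = 0.882) | 91.0% | 90.0% | 87.7% |
| 16 | 93.9% | 93.1% | 91.2% |
| 15 | 96.3% | 95.7% | 94.2% |

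At 26 per group the shortfall against 90% is 90.0 − 87.7 = 2.3 to 90.0 − 86.5 = 3.5 points, and only if 29 was the bare minimum. The largest SD that keeps 90% at 26 per group is 16.4 points. The protocol claims at least 90%, so a smaller planning SD, and hence no cost at all, is also consistent with it.

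**4. What replacement would take.** Patients to start per group for 29 evaluable, 29 / (1 − q) rounded up: q = 5% gives 31 (62 in total), q = 10% gives 33 (66 in total). Both totals are far below the roughly 200 candidates to be screened.

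**5. How wide the window for loss is.** Patients enter after at least 4 weeks of stability, recruitment is 1 week before polysomnography, and OSLER shares the polysomnography visit. An exacerbation before actigraphy uses up no sleep test. Loss of the kind described is confined to the days between actigraphy and polysomnography, plus failed recordings.

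**The case for a change.** The best case for a change is that enrolment targets, replacement and test slots belong in a protocol, since an analysis plan cannot supply recruits afterwards. The 200 spirometries serve screening and not loss after inclusion. And even if the flow chart shows how the groups are filled, equal numbers of actigraphies and polysomnographies leave no room for a patient lost between the two. One or two sentences and a few extra slots would settle it.

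Part of this stands. The protocol does not say whether 58 counts patients started or patients evaluable, and on the strict reading the actigraphy count is short by one for each patient lost after that step. But that is a resource count. It does not touch the power statement, which is right for 29 evaluable patients per group.

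The rest does not carry a change. The text fixes 29 per group, and CASIS is a questionnaire that can be scored before any sleep test. Filling both groups from the screened candidates therefore fits everything that is written. A larger loss of power is possible with unequal groups; a 17/41 split would give 83.9% to 85.2% under the assumptions above. It arises only if the stated 29 per group is not followed, and nothing in the text leads there.

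**Conclusion.** The observation is correct: the counts allow for no loss, and no filling or replacement rule appears in the readable text. It does not show an error. No stated figure is wrong, and none of the provisions conflict once 29 is read as evaluable patients per group. The investigators would naturally continue screening until each CASIS group has its 29 polysomnographies, and the flow chart may already show this.

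If a tenth of the patients were lost and nobody replaced, power would be about 2 to 3.5 points below 90% when the planning SD was 17.0 to 17.3 points, and still above 90% when it was about 16 points or less. This rests on a two-sided 5% t-test, a 15-point difference and an assumed 10% loss, none of which the protocol confirms. A replacement sentence or a larger enrolment figure would be a reasonable courtesy to the reader, but the plan does not need it.
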